### 11.5.3. Reporting Standards for Pharmacokinetic

Pharmacokinetic Concentration Data	
PC Windows Non-Linear (WNL) File	PC WNL file (CSV format) for the non-compartmental analysis by Clinical Pharmacology Modelling and Simulation function will be created according to [Insert document name]. Note: Concentration values will be imputed as per GUI_51487
Descriptive Summary Statistics, Graphical Displays and Listings	Refer to IDSL PK Display Standards. Refer to IDSL Statistical Principle 6.06.1. Note: Concentration values will be imputed as per GUI_51487 for descriptive summary statistics/analysis and summarized graphical displays only.
NONMEM/Pop PK File	Not applicable.
Pharmacokinetic Parameter Derivation	
PK Parameter to be Derived by Programmer	The following PK parameters will be derived by the Programmer: C 24 , AUC/Dose, C max /Dose, Ratio of accumulation
Pharmacokinetic Parameter Data	
Is NQ impacted PK Parameters Rule Being Followed	[Modify as required] No. OR Yes, refer to [Standards for Handling NQ Impacted PK Parameters].
Descriptive Summary	Refer to IDSL PK Display Standards.

Statistics, Graphical Displays and Listings	Refer to [Insert document name]
---	---------------------------------

## 11.6. Appendix 6: Derived and Transformed Data

### 11.6.1. General

Multiple Measurements at One Analysis Time Point

 
Mean of the measurements will be calculated and used in any derivation of summary statistics but if listed, all data will be presented.
 
Participants having both High and Low values for Normal Ranges at any post-baseline visit for safety parameters will be counted in both the High and Low categories of “Any visit post-baseline” row of related summary tables. This will also be applicable to relevant Potential Clinical Importance summary tables.
 

Study Day

 
Calculated as the number of days from First Dose Date:           
 
Ref Date = Missing → Study Day = Missing
 
Ref Date < First Dose Date → Study Day = Ref Date – First Dose Date
 
Ref Date ≥ First Dose Date → Study Day = Ref Date – (First Dose Date) + 1
 
 
 

### 11.6.2. Study Population

Demographics
Age

 
GSK standard IDSL algorithms will be used for calculating age where birth date will be imputed as follows:           
 
Any subject with a missing day will have this imputed as day ‘15’.
 
Any subject with a missing date and month will have this imputed as ‘30th June’.
 
 
 
Birth date will be presented in listings as ‘YYYY’.
 

Body Mass Index (BMI)

 
Calculated as Weight (kg) / [Height (m)]
 

Extent of Exposure

 
Number of days of exposure to study drug will be calculated based on the formula:           <math display="block">\text{Duration of Exposure in Days} = \text{Treatment Stop Date} - (\text{Treatment Start Date}) + 1</math> 
 
Subjects who were randomized but did not report a treatment start date will be categorised as having zero days of exposure.
 
The cumulative dose will be based on the formula:           <math display="block">\text{Cumulative Dose} = \text{Sum of (Number of Days x Total Daily Dose)}</math> 
 
If there are any treatment breaks during the study, exposure data will be adjusted accordingly.
 

### 11.6.3. Safety

Adverse Events

 
Gastrointestinal nonspecific symptoms and therapeutic procedures
 

Abdominal discomfort

Abdominal distension
Abdominal pain
Abdominal pain lower
Abdominal pain upper
Abdominal symptom
Abdominal tenderness
Abnormal faeces
Aerophagia
Anorectal discomfort
Bowel movement irregularity
Change of bowel habit
Constipation
Defaecation disorder
Defaecation urgency
Diarrhoea
Discoloured vomit
Epigastric discomfort
Eructation
Faecal volume decreased
Faecal volume increased
Faeces hard
Faeces soft
Flatulence
Frequent bowel movements
Gastrointestinal pain
Gastrointestinal sounds abnormal
Gastrointestinal toxicity
Infrequent bowel movements
Nausea
Non-cardiac chest pain
Oesophageal discomfort
Oesophageal pain
Vomiting
Anorectal swelling
Antacid therapy
Antidiarrhoeal supportive care
Antiemetic supportive care
Breath odour
Chest pain
Colonic lavage
Dysphagia
Early satiety
Gastritis prophylaxis
Gastrointestinal disorder therapy

Gastrointestinal tract irritation
Gastrooesophageal reflux prophylaxis
Glycogenic acanthosis
Hypovolaemia
Laxative supportive care
Malabsorption
Mucous stools
Pernicious anaemia
Post procedural constipation
Post procedural diarrhoea
Post-tussive vomiting
Probiotic therapy
Procedural nausea
Procedural vomiting
Prophylaxis against diarrhoea
Prophylaxis of nausea and vomiting
Regurgitation
Retching
Steatorrhoea
Vomiting projectile

ECG Parameters
RR Interval

 
IF RR interval (msec) is not provided directly, then RR can be derived as :             
 
[1] If QTcB is machine read & QTcF is not provided, then :                 <math display="block">RR = \left[ \left( \frac{QT}{QTcB} \right)^2 \right] * 1000</math> 
 
[2] If QTcF is machine read and QTcB is not provided, then:                 <math display="block">RR = \left[ \left( \frac{QT}{QTcF} \right)^3 \right] * 1000</math> 
 
 
 
If ECGs are manually read, the RR value preceding the measurement QT interval should be a collected value THEN do not derive.
 

Corrected QT Intervals

 
When not entered directly in the eCRF, corrected QT intervals by Bazett's (QTcB) and Fredericia's (QTcF) formulas will be calculated, in msec, depending on the availability of other measurements.
 
IF RR interval (msec) is provided then missing QTcB and/or QTcF will be derived as :                 <math display="block">QTcB = \frac{QT}{\sqrt{\frac{RR}{1000}}} \qquad QTcF = \frac{QT}{\sqrt[3]{\frac{RR}{1000}}}</math> 
 

#### 11.6.4. Pharmacokinetic

General

• The PK Plasma Concentration Population will include all subjects who undergo plasma PK sampling and have evaluable PK assay results for the study drug.

• Data from subjects who have major protocol deviations will be excluded from PK concentration summary, PK parameter summary and statistical comparisons but will be included in the Listing and flagged.

• This population will be used for listing PK concentrations, parameters, calculating PK parameters and plotting of individual concentration-time files.

• If during clinical phase, 3 consecutive samples in any phase i.e.(Absorption, Distribution and Metabolism / Excretion) are found to be missing then data for that subject will not be included in PK and statistical analysis and only the concentration data of that subject(s) will be presented

• Calculation of Pharmacokinetic Parameter Values Not Described in Section 9 (refer to GUI_51487 for pharmacokinetic analysis information)

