The totality of preliminary PK and safety/tolerability data to date shows the MAD 320 mg QD dose is clinically and scientifically reasonable (see Section 3.2.2 for full details). Specifically, GSK3640254 following single dose administration ultimately showed a plateauing of exposure at the 700 mg dose. On Day 14, the mean C_{max} for the MAD 200 mg dose (1841 ng/ml in Cohort 5) approximated that seen in the SAD at 400 and 700 mg doses (1881 and 1761 ng/ml, respectively). Since the current protocol does not permit a dose in the MAD to surpass the C_{max} studied in the SAD, the ViiV/ GSK Dose Escalation Committee opened the Expansion Cohort (currently ongoing) with a 200 mg dose (See Figure 1) at the conclusion of Cohort 5. Briefly, there have been no significant clinical safety/tolerability findings in the SAD or MAD through May 7, 2018. Preliminary ongoing data review show no deaths or SAEs. There have been 4 individual AEs leading to discontinuation. There have been 10 individual AEs related to blinded study medication. Preliminary review of blinded safety data for the: 1) SAD show 17 subjects experienced 60 individual AEs (58 Grade 1; Two Grade 2) and 2) MAD show 23 subjects experienced 79 individual AEs (77 Grade 1; Two Grade 2). The two most frequent AE SOCs have been Nervous System and Gastrointestinal Disorders without a dose/AE relationship. Subjects recruited for the 320 mg QD Cohort will have the same inclusion/exclusion criteria, have the same study and subject stopping criteria, and undergo the same intensive safety evaluation as previously treated subjects in the MAD. Combined, based upon the preliminary safety and PK data gathered to date (see Section 3.2.2 for full details) subjects will be adequately monitored.

Section # and Name	Description of Change	Brief Rationale
Synopsis Section 5.1 Overall Design	Figure 1 changed and MAD Expansion Cohort Dose added	The actual doses for all Cohorts and Periods updated for the SAD and MAD
Section 3.2.2 Preliminary Safety and PK data in Current Study	Preliminary Safety and PK data from SAD and MAD updated/added	The clinical and PK data is needed to justify the rationale for supporting a proposed dose of 320 mg QD in the MAD (Cohort 6)
Section 3.3 Benefit Risk Assessment	Preliminary Safety and PK data from SAD and MAD updated/added	The clinical and PK data is needed to justify the rationale for supporting an unchanged benefit risk assessment for a proposed dose of 320 mg QD in the MAD (Cohort 6)

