ECG= Electrocardiogram; AUC(0-24) = Area under the plasma concentration time curve from zero to 24; AUC(0-inf) = Area under the concentration-time curve from time zero (pre-dose) extrapolated to infinite time; C_{max}= Maximum observed concentration; t_{max}= Time of occurrence of C_{max}; t_{1/2}= Apparent terminal phase half-life; CL/F= Apparent oral clearance

[figure not shown]
Overall Design:

This study is a Phase 1, double-blind (sponsor-unblinded), randomized, placebo-controlled, single- and repeat-dose escalation study of GSK3640254 in healthy participants.

A summary of the overall study design, including doses, sample size, and order, is presented in [Figure 1](#); Schedule of Activities (SoA) tables are included in Section 2.

The proposed dosing schedule is designed to investigate single oral doses of GSK3640254 initially in Part 1 and then, at a suitable cross-over point (described below), repeated once-daily oral dosing of GSK3640254 in Part 2. All doses will be administered immediately following a moderate fat meal (approximately 600 calories with approximately 30% of calories from fat), unless otherwise indicated.

Figure 1 Phase 1 Study in Healthy Participants using planned doses of GSK3640254

Note: A=active, P=placebo. The doses shown here were/are being completed. Amendment 04 proposes to evaluate a 320 mg Daily dose in MAD Cohort 6.

Number of Participants:

A total of approximately 72 randomized participants will be targeted for the entire study. Part 1 will randomize approximately 16 participants, 8 participants in each of Cohort 1 and Cohort 2. Part 2 will randomize approximately 56 participants, 8 participants in each of Cohorts 3 to 6 and 24 participants in the Expansion Cohort.

If participants prematurely discontinue the study in the single ascending dose (SAD), they may be replaced at the discretion of the Sponsor in consultation with the investigator. The replacement participants will be assigned to the same treatment sequence, starting where the prior participant prematurely discontinued. Previously administered doses will not be repeated by replacement subjects if dose escalation criteria are met.

If participants prematurely discontinue the study in the MAD, they may be replaced at the discretion of the Sponsor in consultation with the investigator. The replacement participants will be assigned to the same treatment in the same Cohort where the prior participant prematurely discontinued.

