#### 4. ANALYSIS POPULATIONS

Population	Definition / Criteria	Analyses Evaluated
Screened	
 
All participants who were screened for eligibility
 
	
 
Study Population
 

Enrolled	
 
All participants who passed screening and entered the study.
 
Note screening failures (who never passed screening even if rescreened) and participants screened but never enrolled into the study (Reserve, Not Used) are excluded from the Enrolled population, as they did not enter the study.
 
	
 
Study Population
 

Safety	
 
All randomized participants who received at least one dose of study treatment.
 
This population will be based on the treatment the subject actually received for each respective cohort/period .
 
	
 
Study Population
 
Safety
 

Pharmacokinetic (PK) Concentration	
 
Part 1 (SAD) The PK Concentration Population will include all participants who undergo plasma PK sampling and have at least one evaluable concentration during the single dose phase of the study Part 1.
 
Part 2 (MAD) The PK Concentration Population will include all participants who undergo plasma PK sampling and have at least one evaluable concentration during the repeat dose phase of the study Part 2.
 
	
 
PK concentration Listing
 
PK individual concentration-time data plots
 

Pharmacokinetic (PK) Parameter	
 
Part 1 (SAD) The PK Parameter Population will include all participants who undergo plasma PK sampling and have evaluable PK parameters estimated during the single dose phase of the study Part 1.
 
Part 2 (MAD) The PK Parameter Population will include all
 
	
 
PK parameter listing
 
PK mean/median concentration-time data plots
 
PK parameter
 

Population	Definition / Criteria	Analyses Evaluated
	participants who undergo plasma PK sampling and have evaluable PK parameters estimated during the repeat dose phase of the study Part 2.	summary 
 
• Dose proportionality
 
• Accumulation ratio analysis and steady state analysis for Part 2
 

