## 11.7. Appendix 7: Reporting Standards for Missing Data

### 11.7.1. Premature Withdrawals

Element	Reporting Detail
General	
 
• Subject study completion was defined as complete all phases of the study including the follow-up visit.
 
• Withdrawn subjects may be replaced in the study, if applicable, at the discretion of the sponsor in consultation with the investigator.
 
• All available data from subjects who were withdrawn from the study will be listed and all available planned data will be included in summary tables and figures, unless otherwise specified.
 
• All subjects who withdraw prematurely from the study/study drug will be documented and the reason for their withdrawal recorded in the final Clinical Pharmacology Study Report (CPSR).
 
• In the event that the study is prematurely discontinued, all available data will be listed and a review carried out by the study team to assess which statistical analyses are still considered appropriate.
 

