### 11.7.2. Handling of Missing Data

Element	Reporting Detail
General	
 
• Missing data occurs when any requested data is not provided, leading to blank fields on the collection instrument: 
 
○ These data will be indicated by the use of a “blank” in subject listing displays. Unless all data for a specific visit are missing in which case the data is excluded from the table.
 
○ Answers such as “Not applicable” and “Not evaluable” are not considered to be missing data and should be displayed as such.
 
 
 

Outliers	
 
• Any participants excluded from the summaries and/or statistical analyses will be documented along with the reason for exclusion in the clinical study report.
 

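### A three-sample gap in one PK profile removes the whole participant from PK analysis, including the participant's other complete profiles (SAP 11.6.4)

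*SAP*

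**What the plan says.** SAP 11.6.4 (Appendix 6) sets the trigger as "3 consecutive samples in any phase i.e.(Absorption, Distribution and Metabolism / Excretion". If three such samples "are found to be missing then data for that subject will not be included in PK and statistical analysis". For such a participant, a display of the measured concentrations is all that remains. Nothing confines the exclusion to the period, day or parameter affected.

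Other parts of the SAP bear on the same data:

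- **Section 4** admits to the Part 1 PK Parameter Population participants who "have evaluable PK parameters estimated during the single dose phase of the study Part 1", with matching wording for Part 2. This population feeds the parameter summaries, dose proportionality, accumulation and steady-state analyses. No three-sample condition appears.
- **Appendix 1 (11.1)** lists one ground for exclusion from the PK parameter summaries: failing an eligibility criterion.
- **11.7.1** says of withdrawn participants that "all available planned data will be included in summary tables and figures, unless otherwise specified".
- **11.7.2** gives the general definition: "Missing data occurs when any requested data is not provided, leading to blank fields on the collection instrument". It does not say whether samples that never fell due count.

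On replacements in the SAD, the protocol synopsis says: "Previously administered doses will not be repeated by replacement subjects if dose escalation criteria are met".

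**The concern.** Participants contribute more than one profile. Each SAD participant receives placebo once in four periods, and so has three active single-dose profiles. Each active MAD participant has separate Day 1 and Day 14 parameter sets. A gap in one profile says nothing about the quality of the others, and often nothing about several parameters of the same profile.

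With six on active drug per dose, each lost participant matters. The loss would run through the descriptive summaries, the power model for dose proportionality and, in Part 2, the accumulation and steady-state models. The final N could also depend on which passage the programmer follows. Protocol 7.4 gives the sponsor's statistician and PK staff access to unblinded data, so that choice is better fixed in the text.

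**Working it through.** **1. The plan's own figure.** Protocol 5.1 (Table 5) has four sequences with two participants each, and in every period exactly one sequence is on placebo. Active per period = 3 × 2 = 6 and placebo = 2, as stated. Active profiles per participant = 4 − 1 = 3. A gap in one leaves two others.

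**2. Gaps that trigger the rule with no question about samples not due** (sampling times from protocol Section 2):

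| Last sample taken (SAD, or MAD after the Day 14 dose) | Later samples missed | Rule triggered? |
|---|---|---|
| 24 h | 48, 72, 96 h (3) | Yes |
| 48 h | 72, 96 h (2) | No |
| 72 h | 96 h (1) | No |

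- *Late gap, SAD.* Cmax, C24 and AUC(0-24) are complete at that dose. AUC(0-inf), t1/2 and CL/F depend on the lost samples. The rule drops all of them, and up to two other doses.
- *Late gap, MAD.* AUC(0-τ), Cmax and Cτ on Day 14 are complete, and only t1/2 needs the later samples. The rule drops both days.
- *Early gap, SAD.* Missing 0.5, 1 and 1.5 h is three consecutive absorption samples. The shortest SAD tmax in protocol Table 3 is 2 h, so Cmax would probably stand, while tlag and the AUCs are affected. The rule again drops everything.

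**3. Precision.** For a geometric mean, 95% CI factor = exp[ t(0.975, n−1) × SDlog / √n ], with SDlog = √ln(1 + CV²).

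| CV | SDlog | n = 6 (t = 2.571) | n = 5 (t = 2.776) |
|---|---|---|---|
| 35% (assumed) | 0.340 | ×/÷ 1.43 | ×/÷ 1.53 |
| 50% (400 mg Cmax, protocol Table 3) | 0.472 | ×/÷ 1.64 | ×/÷ 1.80 |

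On the log scale the interval is wider by (2.776/√5) / (2.571/√6) = 1.242 / 1.050 = 1.18, whatever the CV.

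**4. Share lost per deletion.** At a SAD dose or in a MAD cohort with six on active drug: 1/6 = 16.7%. At MAD 200 mg, Cohort 5 and the Expansion Cohort give 6 + 18 = 24 on active drug, so 1/24 = 4.2%.

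**5. Dose-proportionality slope, Part 2.** With n = 6, 6, 24, 6 at 50, 100, 200 and 320 mg and an assumed CV of 40%, the 90% CI half-width is t(0.95, N−2) × SDlog / √Σ(x − x̄)², where x is log dose. This gives 0.176. It becomes 0.186, 0.177 or 0.180 after one deletion at 50, 200 or 320 mg.

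**6. Departures between periods, only if samples never collected count as missing.** Completed active profiles at stake: 0 or 1 on leaving before Period 2; 1 (Sequences 1 and 2) or 2 (Sequences 3 and 4) before Period 3; 2, or 3 in Sequence 4, before Period 4.

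**The case against.** The strongest reply is that the rule was never meant to reach this far. Its phases are those of a profile after dosing, and a dose never given has none. Withdrawal has its own section, 11.7.1, which keeps the available data. Counting samples never collected as missing would also exclude every SAD replacement, who joins mid-sequence, and so defeat the purpose of replacing anyone. Section 4 leaves evaluable undefined, so 11.6.4 could be its criterion.

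Much of this stands. A reader might infer that anyone who discontinues or is replaced loses all earlier profiles. The documents do not support that:

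- Leavers who miss one or two samples do not trigger the rule.
- Departures between SAD periods or before MAD Day 14 turn on a definition the SAP does not give, and 11.7.1 points towards retention. Its exception for cases otherwise specified stops it from settling the matter.
- Half of each SAD cohort (Sequences 1 and 2) has only one active dose by the end of Period 2.
- MAD replacements receive the same treatment in the same cohort and supply a new Day 1 profile. In the SAD, not repeating earlier doses is conditional on the escalation criteria being met.

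The frequency is also uncertain. The Amendment 04 rationale reports four adverse events that led to discontinuation, which need not be four participants or all on active drug. It also says "SAD show 17 subjects experienced 60 individual AEs". Against about 16 planned, that makes a replacement likely but does not state one. Protocol Table 3 shows N = 6 for Cmax at every SAD dose, so the preliminary data show no deletion.

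A reader might also infer that the rule removes high-exposure participants and pulls means, slope and CV downwards. No exposure data for discontinued participants are given, and the Amendment 04 rationale reports no link between dose and the two most frequent classes of adverse event.

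The reply does not reach the gaps in step 2 of the working. There the dose was given and the samples were due, yet the text still excludes the participant and not just the affected parameters.

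**Conclusion.** The point holds for gaps within a profile. SAP 11.6.4 is triggered inside one profile but excludes the whole participant. Followed as written, it discards valid parameters in that profile and all of the participant's other complete profiles: up to two other active SAD doses, or MAD Day 1. That does not fit Section 4, Appendix 1 or 11.7.1, and the SAP does not say which governs.

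The size is moderate: an interval about 18% wider on the log scale for each affected group of six, and little at MAD 200 mg. This assumes one deletion per group and an unchanged CV; the 35% is an assumption, the 50% an observed preliminary value. Part of the loss at the dose with the gap would occur under any sensible rule, because some parameters there cannot be estimated. Extension to departures between periods or before Day 14 is unresolved, and exposure-related bias is not shown. These are secondary endpoints, but the loss is avoidable and the text should be changed.

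**What to change.** Replace the last sentence of the general rules in SAP 11.6.4 with:

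> If 3 consecutive samples are missing within a profile (subject × period, or subject × day), only the parameters that depend on those samples are set to missing for that profile; all other parameters and profiles of the subject remain in PK summaries and models. Samples not due because of withdrawal, or because a replacement joined later, do not count as missing.

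Add a line that this rule, Section 4 and 11.7.1 are to be read consistently, and refer to the rule in Appendix 1.

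The cost is a few sentences and a flag per profile and parameter in place of one per subject. No new data are needed. The Part 1 power model and the accumulation model already carry a random subject effect and accept unbalanced data.
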